8.2.2. Adverse Event Summaries

An overall summary of AEs by treatment group will include:

- Number (%) of subjects reporting any TEAEs
- Number (%) of subjects reporting any treatment-related TEAEs
- Number (%) of subjects reporting any SAEs
- Number (%) of subjects reporting any Grade 3 or 4 TEAEs
- Number (%) of subjects who temporarily interrupted study treatment because of TEAEs
- Number (%) of subjects who permanently discontinued study treatment because of TEAEs
- Number (%) of subjects who had a fatal TEAE

The following summaries will be produced by MedDRA term (if 2 or fewer subjects appear in a table, a listing may be appropriate):

- Summary of TEAEs by SOC and PT
- Summary of TEAEs by PT in decreasing order of frequency
- Summary of TEAEs by SOC, PT, and maximum severity
- Summary of treatment-related AEs by SOC and PT
- Summary of treatment-related AEs by PT in decreasing order of frequency
- Summary of treatment-related AEs by SOC, PT, and maximum severity
- Summary of TEAEs leading to death by SOC and PT
- Summary of treatment-emergent SAEs by SOC and PT
- Summary of treatment-related SAEs by SOC and PT
- Summary of TEAEs leading to interruption of study treatment by SOC and PT
- Summary of TEAEs leading to discontinuation of study treatment by SOC and PT
- Summary of TEAEs requiring concomitant medications by SOC and PT
- Summary of treatment-emergent non-SAE by SOC and PT

8.3. Clinical Laboratory Tests

8.3.1. Laboratory Value Definitions

All laboratory assessments will be performed using a central laboratory except for urine pregnancy tests (as applicable). Laboratory values and change from baseline values will be summarized descriptively by visit, and non-numeric test values will be tabulated when necessary.

The baseline value will be determined using the nonmissing values collected before the first application, prioritizing scheduled assessments for baseline identification over unscheduled visits. The last record before administration in the highest priority will be considered the baseline record. For baseline laboratory candidates with the same date and time in the same priority category, additional rules may be provided after consultation with the medical monitor to delineate which value will be defined as baseline.

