3.2. Subject Exclusion Criteria

A subject who meets any of the following criteria will be excluded from the study:

1. Subjects with evidence of acute acute or chronic infections.
2. Use of topical treatments for AD (other than bland emollients) within 2 weeks of baseline.
3. Systemic immunosuppressive or immunomodulating drugs (eg, oral or injectable corticosteroids, methotrexate, cyclosporine, mycophenolate mofetil, azathioprine) within 4 weeks or 5 half-lives of baseline (whichever is longer).
4. Subjects with other dermatologic disease besides AD whose presence or treatments could complicate the assessment of disease (eg, psoriasis).
5. Subjects with a history of other diseases besides dermatologic disorders (eg, other autoimmune diseases) taking treatments that could complicate assessments.
6. Subjects with cytopenias at screening, defined as:
 - a. Leukocytes $< 3.0 \times 10^9/L$.
 - b. Neutrophils $<$ lower limit of normal.
 - c. Hemoglobin $< 10 \text{ g/dL}$.
 - d. Lymphocytes $< 0.8 \times 10^9/L$.
 - e. Platelets $< 100 \times 10^9/L$.
7. Subjects with severely impaired liver function (Child-Pugh Class C) or end-stage renal disease on dialysis or at least 1 of the following:
 - a. Serum creatinine $> 1.5 \text{ mg/dL}$.
 - b. Alanine aminotransferase or AST $\geq 1.5 \times$ upper limit of normal (ULN).

8. Subjects taking potent systemic CYP3A4 inhibitors or fluconazole within 2 weeks or 5 half-lives, whichever is longer, before the baseline visit (topical agents with limited systemic availability are permitted, see [Appendix C](#)).
9. Subjects who have previously received JAK inhibitors, systemic or topical (eg, ruxolitinib, toficitinib, baricitinib, filgotinib, lestaurtinib, pacritinib).
10. Women who were pregnant or breastfeeding within 4 months before screening.
11. Current or recent history (< 30 days before screening and/or < 45 days before randomization) of a clinically meaningful bacterial, fungal, parasitic, or mycobacterial infection.
12. Positive serology test results for hepatitis B surface antigen or core antibody, or for hepatitis C virus antibody with detectable hepatitis C RNA at screening or human immunodeficiency virus (HIV) antibody.
13. Current clinically meaningful viral infection (eg, eczema herpeticum).

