5.4.2. Criteria and Procedures for Dose Interruptions and Adjustments of Study Drug

In some circumstances, it may be necessary to temporarily interrupt treatment as a result of AEs or laboratory abnormalities that may have an unclear relationship to study drug. Except in cases of emergency, it is recommended that the investigator consult with the sponsor medical monitor (or other representative of the sponsor) before temporarily interrupting study drug. Additionally, the investigator must obtain approval from the sponsor before restarting study drug that was temporarily interrupted because of an AE or laboratory abnormality.

Individual subjects may have administration interrupted at the discretion of the investigator, in consultation with the sponsor, for AEs or laboratory abnormalities until these have resolved. Subjects MUST have administration interrupted in the following situations:

- The subject develops a Grade 2 increase in ALT ($> 3 \times \text{ULN}$) or AST ($> 3 \times \text{ULN}$), or a Grade 2 decrease in ANC ($< 1.5 \times 10^9/\text{L}$) or platelets ($< 75 \times 10^9/\text{L}$), or a Grade 3 decrease in absolute lymphocyte count ($< 0.5 \times 10^9/\text{L}$). Laboratory abnormalities should be confirmed with repeat testing within 48 hours whenever possible and STAT delivery of the laboratory results requested.
- The subject develops a Grade 3 or higher laboratory abnormality, with the exceptions of lipase (in which case a Grade 4, $> 5 \times \text{ULN}$, results in discontinuation of study medication) or any asymptomatic triglyceride, cholesterol, or amylase elevations. Laboratory abnormalities should be confirmed with repeat testing within a medically indicated timeframe, based upon the investigator's judgment and in collaboration with the sponsor's medical monitor, and STAT delivery of the laboratory results requested.
- The subject had a Grade 3 or 4 drug-related AE as determined by the investigator.

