9.4.2.2. Clinical Laboratory Tests

Laboratory test values outside the normal range will be assessed for severity based on the normal ranges for the clinical reference laboratory. The incidence of abnormal laboratory values and shift tables relative to baseline will be tabulated.

Laboratory data will be classified into Grades 1 through 4 using CTCAE v4.03. The following summaries will be produced for the laboratory data:

[figure not shown]
- Number and percentage of subjects with worst postbaseline CTCAE grade (regardless of baseline value). Each subject will be counted only for the worst grade observed postbaseline.
- Shift tables from baseline to the worst postbaseline value using CTCAE grade.
- For laboratory parameters where CTCAE grades are not defined, shift tables to the worst postbaseline value using the low/normal/high classifications based on laboratory reference ranges.

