5. STATISTICAL METHODOLOGY

5.1. General Methodology

Unless otherwise noted, SAS® software (SAS Institute Inc, Cary, NC; Version 9 or later) will be used for the generation of all tables, graphs, and statistical analyses. Descriptive summaries for continuous variables will include, but not be limited to, the number of observations, mean, standard deviation, median, minimum, and maximum. Descriptive summaries for categorical variables will include the number and percentage of subjects in each category.

During the DB period, the safety population will be used for all safety analyses, and the ITT population will be used for all efficacy analyses. [REDACTED]

Interim analyses are planned for this Protocol as defined in [Section 9](#).

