8.3.2. Laboratory Value Summaries

Clinical laboratory tests, including hematology and serum chemistry, will be performed at the Protocol-specified visits. If specific safety issues arise, additional unscheduled laboratory tests/analyses may be performed at the discretion of the investigator.

All test results and associated normal ranges from central laboratories will be reported in SI units. All tests with numeric values will have a unique unit per test. Any laboratory test results and associated normal ranges from local laboratories will be converted to SI units.

When there are multiple laboratory nonmissing values for a subject's particular test within a visit window, the laboratory value with the smallest laboratory sequence number will be used in by-visit summaries.

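### The SAP omits the protocol's CTCAE-grade and shift laboratory tables for the double-blind period, and SAP 10.1 does not record the changes from protocol-defined analyses

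*SAP*

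**What the plan says.** **Protocol 9.4.2.2** grades laboratory data by CTCAE v4.03 and commits to three outputs:

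- "Number and percentage of subjects with worst postbaseline CTCAE grade (regardless of baseline value"), with each subject counted once;
- "Shift tables from baseline to the worst postbaseline value using CTCAE grade";
- for parameters without a CTCAE grade, "shift tables to the worst postbaseline value using the low/normal/high classifications based on laboratory reference ranges".

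**SAP 8.3.1** states that "Laboratory values and change from baseline values will be summarized descriptively by visit". **SAP 8.3.2** adds that, when a visit window holds several values, "the laboratory value with the smallest laboratory sequence number will be used in by-visit summaries". Neither section mentions grades, worst values or shifts. **SAP 5.1** defines descriptive summaries of continuous variables as including "the number of observations, mean, standard deviation, median, minimum, and maximum".

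**SAP Appendix A** lists, for the double-blind period, one hematology table (3.1.3.1) and one chemistry table (3.1.3.5), both plain value summaries. For the open-label period it lists 3.2.3.1 and 3.2.3.5 of the same kind, plus 3.2.3.8, a CTC-grade shift table for chemistry.

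**SAP 10.1**, the place for changes to protocol-defined analyses, is marked as not applicable.

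**The concern.** Protocol 1.7.5 describes anemia, thrombocytopenia and neutropenia as dose-related with the oral drug. This is a vehicle-controlled dose-ranging trial of the same molecule, so counts of subjects by worst grade and by shift, set side by side by arm, are the natural descriptive check for a topical counterpart of that pattern. The protocol promised those counts. If the SAP is followed as written, they are not produced for the randomized period, which is the only part of the study with a concurrent vehicle arm.

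The change log raises a separate question of record. A reader who relies on SAP 10.1 would conclude that the analyses are those of the protocol. The model for the primary and key secondary comparisons has changed, and the laboratory summaries have gone without comment.

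**Working it through.** No sample size, power or alpha figure bears on this point, so there is no document figure to reproduce. The check is a comparison of texts and a count.

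**Step 1. Coverage.** Inputs: the three summaries in Protocol 9.4.2.2 and the table list in SAP Appendix A.

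| Promised summary | Double-blind hematology | Double-blind chemistry | Open-label hematology | Open-label chemistry |
|---|---|---|---|---|
| Worst CTCAE grade | none | none | none | none |
| CTCAE shift to worst | none | none | none | 3.2.3.8 |
| Low/normal/high shift | none | none | none | none |

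3 summaries × 2 classes × 2 periods = 12 cells, of which 1 is planned. Double-blind: 0 of 3 × 2 = 6. Hematology: 0 of 6. This is an upper count of what is owed, because the third row applies only to parameters without a CTCAE grade. Leaving that row out gives 1 of 2 × 2 × 2 = 8, with 0 of 4 for the double-blind period and 0 of 4 for hematology.

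**Step 2. What reaches the adverse event tables anyway.** Protocol 5.4.2 makes interruption mandatory at stated laboratory grades. Under Protocol 8.1.1 and 8.2, an abnormality that requires a change in study drug is an adverse event. Combining the two:

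| Parameter | Mandatory interruption from | Grades not captured by that route |
|---|---|---|
| Neutrophils (ANC) | Grade 2 | 1 |
| Platelets | Grade 2 | 1 |
| Lymphocytes | Grade 3 | 1 and 2 |
| Hemoglobin (not named; general rule) | Grade 3 | 1 and 2 |
| ALT, AST | Grade 2 | 1 |
| Other graded parameters (general rule) | Grade 3 | 1 and 2 |

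The exceptions to the general rule (lipase, and asymptomatic triglyceride, cholesterol or amylase elevations) concern analytes that are not in the scheduled panel of Protocol Table 3. Events captured by this route are counted by arm in planned tables: TEAEs by maximum severity (3.1.2.4), TEAEs leading to interruption (3.1.2.14) and, where applicable, the Grade 3 or 4 line of the overall summary (SAP 8.2.2). The grades in the last column reach those tables only if they cause symptoms, are judged clinically meaningful, need therapy or otherwise change study drug.

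**Step 3. Whether the by-visit summaries fill the remainder.** A fall shared by most subjects in an arm would show in the mean and median. A fall in a few subjects can be diluted in the mean. The minimum, whether of the value or of the change from baseline, describes one subject and does not say how many moved or by how many grades. The by-visit tables therefore do not give the promised counts.

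**Step 4. Change log.**

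| Analysis | Protocol | SAP |
|---|---|---|
| Primary | ANOVA with LOCF (9.4.1.2) | MMRM (7.3.1); ANOVA with LOCF kept as sensitivity (7.3.3) |
| Key secondary | Similar ANOVA (9.4.1.3) | Similar MMRM (7.4.1) |
| Responder endpoints, optional test | Cochran-Mantel-Haenszel (9.4.1.3) | Logistic regression (7.4.2) |
| Laboratory | Three grade and shift summaries (9.4.2.2) | By-visit values and changes (8.3) |

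All four rows differ. SAP 10.1 records none of them.

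**The case against.** **The omission may not be a decision.** The SAP is written on the basis of the protocol and does not revoke 9.4.2.2. SAP 8.3.1 does not say that by-visit summaries are the only ones. Appendix A calls its list a guideline and refers to standard safety tables that were not supplied. The laboratory table numbers have gaps, and the lone 3.2.3.8 has no double-blind counterpart, which looks more like lost entries than a choice. This stands as an explanation, but it leaves the SAP without the tables.

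**A reader might infer that no graded per-subject view of hematology is planned at all.** The documents do not support that. The end of the listings is not in the text available for review, so a graded subject listing cannot be excluded. Such a listing would still not replace counts by arm.

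**A reader might infer that clinically important cytopenias would go uncounted.** Step 2 shows otherwise: abnormalities that force interruption are adverse events and are tabulated by arm.

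**A reader might infer that the one-value-per-window rule discards the worst values.** That is mostly wrong. Protocol 5.4.2 says "Laboratory abnormalities should be confirmed with repeat testing within 48 hours whenever possible", and the value that triggers the repeat would ordinarily carry the lower sequence number and be kept. Only a still worse repeat could drop out, and the rule is limited to by-visit summaries. It matters here only because the added tables need their own definition of worst.

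**On severity:** the dose-related cytopenias in Protocol 1.7.5 come from oral dosing, no data are lost, and no primary or key secondary conclusion is affected. All of that is correct and limits the weight of the point.

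**Conclusion.** The point holds as an unreconciled difference between protocol and SAP that should be fixed. No graded or shift laboratory summary table is planned for the double-blind period, and none for hematology in either period; one of 12 possible tables is planned. The practical loss is by-arm counts of mainly lower-grade change, including hemoglobin falls below Grade 3, in the only vehicle-controlled period. The benefit of restoring them is descriptive.

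The SAP 10.1 entry is wrong on its face but is a record error. A reader might take it to mean that the deciding analysis is unclear. It is not: the SAP names one primary model, gives a missing-at-random basis for it in 7.1.1, and keeps ANOVA with LOCF as a sensitivity analysis.

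The conclusion assumes that the unsupplied standard safety tables do not already provide the three summaries for this study, and that none of the three Administrative Changes cited in SAP 2.1, which were not supplied, records the analysis changes. If either assumption fails, a cross-reference in the SAP settles that part.

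**What to change.** 1. Add to SAP 8.3.2 and Appendix A, for the double-blind period, by arm, for hematology and chemistry: worst postbaseline CTCAE grade, shift from baseline to worst CTCAE grade, and low/normal/high shift to worst value for parameters without a grade. State that worst is taken over all postbaseline double-blind values, including repeat and unscheduled tests. Alternatively, record and justify the removal of these summaries in SAP 10.1.
2. Replace the current SAP 10.1 entry with the move from ANOVA with LOCF to MMRM for the primary and key secondary analyses and the optional move from Cochran-Mantel-Haenszel to logistic regression, each with its reason, unless an Administrative Change already does so.

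Cost: a few standard tables from data already collected, a short addition to SAP 8.3.2 and one entry in SAP 10.1. No new data, visits or subjects are needed. Adding the tables needs no protocol amendment, because it restores what the protocol already says.

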8.3.2. Laboratory Value Summaries

Clinical laboratory tests, including hematology and serum chemistry, will be performed at the Protocol-specified visits. If specific safety issues arise, additional unscheduled laboratory tests/analyses may be performed at the discretion of the investigator.

All test results and associated normal ranges from central laboratories will be reported in SI units. All tests with numeric values will have a unique unit per test. Any laboratory test results and associated normal ranges from local laboratories will be converted to SI units.

When there are multiple laboratory nonmissing values for a subject's particular test within a visit window, the laboratory value with the smallest laboratory sequence number will be used in by-visit summaries.

8.4. Vital Signs

Values at each scheduled visit, change, and percent change from baseline for vital signs, including SBP, DBP, pulse, respiration rate, and body temperature will be summarized descriptively.

Criteria for clinically notable vital sign abnormalities are defined in [Table 6](#). The abnormal values for subjects exhibiting clinically notable vital sign abnormalities will be listed along with their assigned treatment group. Alert vital signs are defined as an absolute value outside the defined range and percentage change greater than 25%. The abnormal values for subjects exhibiting alert vital sign abnormalities will be listed.

Table 6: Criteria for Clinically Notable Vital Sign Abnormalities

Parameter	Raw Value	Percent Change From Baseline
SBP	90-150 mmHg	± 25%
DBP	50-90 mmHg	± 25%
Pulse	45-100 beats/min	± 25%
Respiration rate	8-20 breaths/min	± 25%
Temperature	35.5°C-38.0°C	± 25%

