7.5.3. Vital Signs

Vital sign measurements include blood pressure, pulse, respiratory rate, and body temperature. Blood pressure and pulse will be taken with the subject in the sitting position after 5 minutes of rest. Clinically notable abnormalities that are considered clinically significant in the judgment of the investigator are to be reported as AEs.

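### The vital-sign alert rule in SAP 8.4 requires a change of more than 25% as well as an out-of-range value, so no fever can enter the alert listing

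*SAP*

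**What the plan says.** SAP 8.4 covers five parameters, "including SBP, DBP, pulse, respiration rate, and body temperature will be summarized descriptively", and the summaries include "percent change from baseline".

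Table 6 then gives each parameter a raw-value range and a percent-change limit. The limit is ± 25% in all five rows. The temperature range is 35.5°C to 38.0°C.

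Two listings follow from this:

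- Clinically notable values: "The abnormal values for subjects exhibiting clinically notable vital sign abnormalities will be listed along with their assigned treatment group". The criteria are those of Table 6, but the text does not say whether one column is enough or both are needed.
- Alert values: "Alert vital signs are defined as an absolute value outside the defined range and percentage change greater than 25" per cent. For these, "The abnormal values for subjects exhibiting alert vital sign abnormalities will be listed".

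Section 8.4 makes no exception for temperature and offers no absolute-change alternative. Separately, Protocol 7.5.3 says of vital signs: "Clinically notable abnormalities that are considered clinically significant in the judgment of the investigator are to be reported as AEs".

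**The concern.** The two alert conditions are joined by a conjunction, so both must be met. A 25% relative change is attainable for blood pressure, pulse and respiration rate. Body temperature in degrees Celsius varies within a band that is narrow relative to its level, so the same percentage is a very different demand there.

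If no fever can satisfy the rule, the temperature part of the alert listing has no fevers in any arm by definition, whatever happens in the trial. The rule exists to pick out individual values, and for this parameter it would not do so upward. The drug inhibits JAK signalling and the protocol excludes subjects with active infection, so raised temperature is a value that a safety reader may want to see subject by subject.

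**Working it through.** **Inputs.** All are from SAP 8.4 and Table 6: the alert rule (outside the range, and a change above 25%); the ± 25% change from baseline; and the ranges SBP 90–150 mmHg, DBP 50–90 mmHg, pulse 45–100 beats/min, respiration 8–20 breaths/min, temperature 35.5–38.0°C. The defined range in the alert rule is taken to be the raw-value column of Table 6. The SAP states no resulting alert threshold, so there is no planned figure to reproduce first.

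**Step 1: reading needed for an upward temperature alert.** Threshold = 1.25 × baseline.

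- Baseline 35.5°C: 1.25 × 35.5 = 44.375, so above 44.4°C
- Baseline 37.0°C: 1.25 × 37.0 = 46.25°C
- Baseline 38.0°C: 1.25 × 38.0 = 47.5°C

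The lowest in-range baseline is the most favourable case, and it still needs more than 44.4°C.

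**Step 2: percent change produced by high readings.** Change = 100 × (reading / baseline − 1).

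- From 37.0°C: 39°C gives 5.4%, 40°C gives 8.1%, 41°C gives 10.8%, 42°C gives 13.5%
- From 35.5°C: 42°C gives 18.3%, 43°C gives 21.1%
- Across the whole range, 35.5°C to 38.0°C: 7.0%

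**Step 3: baseline that would make a fever an alert.** Baseline must be below reading / 1.25. For 40°C that is 40 / 1.25 = 32.0°C, well below the range.

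**Step 4: downward direction.** Threshold = 0.75 × baseline, which is 0.75 × 35.5 = 26.6°C to 0.75 × 38.0 = 28.5°C. A fall of that size could satisfy the rule, but it is not a fever.

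**Step 5: does the scale matter?** In Fahrenheit, a 98.6°F baseline needs more than 1.25 × 98.6 = 123.25°F, or 50.7°C. The result is more extreme, not less.

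**Step 6: the other rows.** The baseline below which a reading just over the upper limit is also a rise of more than 25% is upper limit / 1.25.

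| Parameter | Range | Upper limit / 1.25 | Inside its own range? |
|---|---|---|---|
| SBP | 90–150 | 120 | Yes |
| DBP | 50–90 | 72 | Yes |
| Pulse | 45–100 | 80 | Yes |
| Respiration | 8–20 | 16 | Yes |
| Temperature | 35.5–38.0 | 30.4 | No |

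In the first four rows an ordinary in-range baseline can lead to an alert. Temperature is the only row where it cannot. This pattern would arise if one percentage had been carried down the whole column, although the SAP does not give its reason.

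**The case against.** The strongest reply is that little depends on this listing, and much of that stands.

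- **Fever is visible elsewhere.** Temperature is summarised at each scheduled visit. SAP 5.1 includes the minimum and maximum in continuous summaries, so a high reading at a scheduled visit would show as a group maximum. SAP Appendix A plans tables for this in the double-blind period (3.1.4.4) and the open-label period (3.2.4.4). Abnormalities judged clinically significant become adverse events and are tabulated.
- **Nothing is triggered by alert status.** Its only stated use is a listing. The mandatory interruption criteria in Protocol 5.4.2 rest on laboratory values and drug-related Grade 3 or 4 adverse events.
- **The clinically notable listing may already catch fevers.** A separate alert definition would be redundant if notable values also needed both conditions. A two-tier reading is therefore natural: either column for notable, both for alert. On that reading, any temperature above 38.0°C is listed with its treatment group.

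The last point is plausible, but the SAP does not state it. A reader might equally infer that Table 6 pairs the columns for the notable listing, so that both listings miss every fever. The text does not support that as fact either: the join is simply unspecified.

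None of this makes the alert rule work for temperature. Adverse-event capture depends on investigator judgment, and a by-visit maximum does not identify the subject.

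**Conclusion.** The point holds as a minor defect in a safety listing. Under the rule as written, no fever can enter the alert listing, because even the most favourable in-range baseline requires more than 44.4°C. This rests on two assumptions the documents do not supply: that such temperatures do not occur in living subjects, and that baselines lie in or near 35.5–38.0°C. The result is the same at every baseline in that range.

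Three stronger readings go too far. The temperature rule is not always false, since a fall below roughly 26.6–28.5°C would meet it. Fever detection in the trial is not lost, because the by-visit summaries and adverse-event reporting remain. It is also not established that the clinically notable listing shares the defect; that follows only if both columns are required.

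No efficacy result, alpha, power or subject management is affected.

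**What to change.** In Table 6 and the alert definition, remove the ± 25% condition for temperature, so that the SAP's existing range alone decides that row of the alert listing. Alternatively, state that the alert tier does not apply to temperature. Leave the other four rows as they are. Add one sentence saying whether a clinically notable value must meet one Table 6 column or both; this matters for all five parameters. No new threshold is introduced.

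The cost is one table cell, one programming condition and one sentence. The listing may become slightly longer. If one column is enough for a notable value, the alert and notable tiers may also coincide for temperature, in which case the alert tier adds nothing for that parameter. The SAP authors should accept that knowingly or choose the alternative.
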